8 STUDY OBJECTIVES

8.1 Primary Objective

The primary objective is to evaluate the effect of 12 months treatment with BGS649 on bone mineral density (6 months treatment during Study MBGS205).

8.2 Secondary Objectives

8.2.1 Safety Objectives

1. To evaluate the effect of BGS649 after 12 months period of treatment with active study drug (6 months treatment during Study MBGS205 and 6 months treatment during Study MBGS206) by dose group on:
 - Bone turnover biomarkers
 - Bone mineral density and bone biomarkers by vitamin D status (Baseline vitamin D from Study MBGS205)
 - Oestradiol levels
 - Testosterone outside upper limit of normal range
 - Prostate specific antigen and haematocrit
 - Blood pressure
 - Adverse events (AEs)
2. To evaluate if any association between changes in bone mineral density after 12 months treatment with BGS649 with end of treatment testosterone and oestradiol levels
3. To collect safety data in subjects switching from placebo arm in Study MBGS205 and treated with 6 months active study drug in Study MBGS206.

8.2.2 Pharmacokinetic Objective

The PK objective is to determine BGS649 concentration by dose in seminal fluid and relationship to plasma PK at the end of treatment.

8.2.3 Efficacy Objectives

1. To follow the change of total testosterone, bioavailable testosterone, LH, and FSH over a total of 12 months administration of BGS649 in those on active treatment in Study MBGS205 and a total of 6 months administration of BGS649 on subjects that were switched from placebo treatment during Study MBGS205
2. Evaluation of percentage of subjects with normalised testosterone after 12 months treatment with BGS649 in those on active treatment in Study MBGS205 and total of 6 months administration of BGS649 on subjects that were on placebo treatment during Study MBGS205

8.2.4 Exploratory Efficacy Objectives

1. To evaluate the effect of 12 months treatment with BGS649 (6 months treatment in Study MBGS205 and 6 months treatment in Study MBGS206) on:
 - Cardiometabolic parameters, body composition, physical activity, grip strength, and sleep pattern; and on sexual functioning, fatigue, and quality of life, assessed by patient reported outcomes (PROs)
 - The association between changes in PROs and changes in body composition, physical activity, grip strength, and sleep
 - The association between changes in testosterone and changes in cardiometabolic parameters, body composition, physical activity, grip strength, sleep, and PROs
2. To evaluate the 6 month efficacy data on subjects on placebo arm in Study MBGS205 treated with active study drug in Study MBGS206 (cardiometabolic parameters, body composition, physical activity, grip strength, sleep, and PROs).

9 INVESTIGATIONAL PLAN

9.1 Overall Study Design and Plan

9.1.1 Description

This is a 6 month, active treatment, extension study, open to subjects who have completed the full 24 week treatment period in Study MBGS205 (a Phase IIb multicentre, double-blind, dose-ranging, randomised, placebo-controlled study evaluating safety and efficacy of BGS649 in male obese subjects with HH).

The main purpose of this study is to evaluate bone mineral density in subjects after 12 months exposure with BGS649. The study will also collect additional BGS649 safety and efficacy data on subjects that were randomised to placebo in Study MBGS205 and have 6 months active drug exposure in Study MBGS206. The study design and schedule of assessments are summarised in [Figure 9-1](#) and [Table 9-1](#), respectively.

Subjects that completed full 24 weeks treatment period of Study MBGS205 will be invited to participate. Informed consent will be taken prior to study procedures being performed. Study participation will comprise of the Extension Study Baseline visit (Week 24 of Study MBGS205), 7 visits during the treatment period up to Week 48 (End of Treatment [EOT]), and a Follow-Up (FU) visit for safety performed at Week 60, 12 weeks after the Week 48/EOT visit. The End of Study is defined as the last visit of the last global subject.

Extension Study Baseline assessment:

The Extension Study Baseline assessment will be performed on a same day as the EOT visit of Study MBGS205. As applicable, EOT assessments of Study MBGS205 will be used for Baseline assessments of Study MBGS206 and do not need to be repeated. The results of liver biochemistry, PSA, haematocrit, and electrocardiogram (ECG) assessments performed at the Baseline visit (EOT of MBGS205) may not be available for eligibility assessment, therefore results of these parameters from last valid visit of Study MBGS205 will be used to enable recruitment and dosing. This includes any of the parameters from last scheduled or unscheduled visit, measured not longer than 1 month before Baseline visit/EOT of MBGS205. Bone density from EOT assessment of MBGS205 will be used for eligibility evaluation for MBGS206.

If results of liver biochemistry, renal function, PSA, haematocrit and ECG measured at Extension Study Baseline visit/EOT of MBGS205 are subsequently found to meet any study discontinuation criteria, the subject will be withdrawn.

During the 24 week treatment period, subjects will take the required dose weekly (\pm 1 day from the time schedule of regular planned dose), starting with the first dose being taken at the baseline visit. The treatment period will consist of up to 24 weekly doses of BGS649. The capsule will be taken orally by the subject with water. Subjects receiving active doses of BGS649 in Study MBGS205 will continue with the same dose in Study MBGS206; this transfer will be handled by the interactive response technology (IRT) and the blind will be

maintained. Subjects receiving placebo in Study MBGS205 will be re-randomised, using IRT, on a 1:1:1 basis to each of the active treatment arms:

- BGS649 [REDACTED] capsules)
- BGS649 [REDACTED]
- BGS649 [REDACTED].

If one or more dosing arms are dropped during the conduct of Study MBGS205 these will not be progressed in Study MBGS206 and subjects switching from placebo will be randomly allocated to available dose arms.

Details of the safety assessments to be performed are provided in [Section 12](#).

[figure not shown]
The safety of the study will also be periodically monitored through a data monitoring committee (DMC) and will include relevant subject data from Study MBGS205 and Study MBGS206.

To ensure adequate safety monitoring, serum total testosterone levels will be evaluated at each visit by an independent unblinded physician (see [Section 9.3.4](#) and [Section 16.3](#)), and if a subject meets the discontinuation criteria (total testosterone ≥ 1500 ng/dL [52 nmol/L] at any 2 consecutive time points throughout both studies the subject will be discontinued from the treatment. This would also include situation when first testosterone value that meets this threshold of ≥ 1500 ng/dL [52 nmol/L] was measured during MBGS205 and consecutive testosterone during study MBGS206.

Details of the efficacy assessments to be performed are provided in [Section 11](#).

PK of BGS649 in seminal fluid will also be evaluated after 12 months of study drug exposure. Seminal fluid PK will be assessed (excluding subjects that are vasectomised or have vasectomy planned during the study period) at the Baseline visit (Week 24 of Study MBGS205) and End of Treatment (Visit 7). Subjects that are discontinued early from the study drug will provide samples for seminal fluid PK at the time of the End of Treatment visit, unless they are not able to provide this sample. Simultaneously with semen PK, plasma PK will be assessed to estimate plasma to semen BGS649 transference.

Figure 9–1 Study Design

DMC=data monitoring committee; W=week

During the 24 week treatment period, [redacted] to total of up to 24 doses. The capsule will be taken orally by the subject with water. Subjects receiving active doses of BGS649 in Study MBGS205 will continue with the same dose in Study MBGS206 and the blind will be maintained at randomisation. Subjects receiving placebo in Study MBGS205 will be randomised on a 1:1:1 basis to each of the active treatment arms. If one or more dosing arms are dropped during the conduct of Study MBGS205 these will not be progressed in Study MBGS206 and subjects switching from placebo will be randomly allocated to available dose arms. The safety of the study will be monitored through a DMC and will include relevant subject data from Study MBGS205 and Study MBGS206.

9.1.2 Schedule of Assessments

The schedule of assessments is presented in [Table 9–1](#).

Table 9–1 Schedule of Assessments

Visit		Treatment Period								
		1	2	3	4	5	6	7 (EOT)	8 (FU)	
Week	Assessments transferred from MBGS205	MBGS206 Baseline ¹ W24	W28 (±2 D)	W32 (±2 D)	W36 (±2 D)	W40 (±2 D)	W44 (±2 D)	W48 (±2 D)	W60 (±2 D)	
Confirmation of written informed consent		X								
Medical/surgical history	X									
Inclusion/exclusion criteria		X								
Treatment allocation ²		X								
Full physical exam: general, prostate and breast exam	X				X			X		
Limited physical exam			X	X		X	X		X	
Blood pressure (SBP, DBP) and heart rate	X		X	X	X	X	X	X	X	
12-Lead ECG	X				X			X		
Clinical laboratory tests³: haematology, blood chemistry, and dipstick urinalysis ⁴ , eGFR by Cockcroft-Gault formula, PSA	X		X	X	X	X	X	X	X	
Cardiometabolic parameters³: HbA1c, fasting lipids (total cholesterol, LDL, HDL, triglycerides), fasting glucose and insulin, hs-CRP, HOMA-IR	X							X		
Bone turnover markers⁵	X				X			X		
Testosterone total ⁶	X		X	X	X	X	X	X	X	
Testosterone bioavailable, oestradiol (total), SHBG, FSH, LH ⁶	X							X		
Semen PK ⁷	X							X		
Plasma PK ⁷	X							X		
Weight, BMI hip and waist measurement	X				X			X		
Body composition using bioimpedance ⁸	X				X			X		
Actigraphy ⁹	X							X		
Grip strength	X				X			X		
PROs: IIEF, BFI, SF-36 QoL PROMIS: SexFS, Fatigue Short Form PGI-S ¹⁰	X				X			X		
DEXA ¹¹	X							X		
Study drug dispensation		X	X	X	X	X	X			
Study drug administration ¹²										
Study drug accountability		X								

Visit		Treatment Period							
		1	2	3	4	5	6	7 (EOT)	8 (FU)
Week	Assessments transferred from MBGS205	MBGS206 Baseline ¹ W24	W28 (±2 D)	W32 (±2 D)	W36 (±2 D)	W40 (±2 D)	W44 (±2 D)	W48 (±2 D)	W60 (±2 D)
AE assessment ¹³	X		X	X	X	X	X	X	X
Concomitant medication	X		X	X	X	X	X	X	X

- 1 Baseline assessment will be performed on a same day as the EOT visit of Study MBGS205. As applicable, EOT assessments of Study MBGS205 will be used for Baseline assessments of Study MBGS206 and do not need to be repeated. The results of liver enzymes, PSA, haematocrit, and ECG assessments performed at the Baseline visit will not be available for eligibility assessment, therefore results of these parameters from last valid visit of Study MBGS205 will be used. This includes any of these parameters from last scheduled or unscheduled visit measure but no longer than 1 month before Baseline visit/EOT of MBGS205.
- 2 Only subjects receiving placebo in Study MBGS205 to be randomised. Subjects already on active in Study MBGS205 will maintain their treatment allocation
- 3 All blood samples are to be collected after 8 hours fasting, after ECG and vital sign measurements have been performed
- 4 A microscopic examination including RBC and WBC or urinary protein will be performed only when dipstick evaluation is positive for WBC and/or blood or protein
- 5 Bone turnover markers include CTx1, osteocalcin, bone alkaline phosphatase, and PINP
- 6 Has to be collected before 11 am. If the sample was inadvertently taken after this time, a retest is allowed after a discussion with the Medical Monitor.
- 7 All subjects that are not vasectomised will be asked to provide a semen sample. Subjects that provided semen sample for PK will also have plasma for PK drawn at the assessment visit Semen sample collection is not required to be the same day as the assessment visit. Therefore, semen PK collection is allowed ± 48 hours around the plasma PK attendance visits.
- 8 Subjects should come well hydrated, drinking water the night before and the morning before the impedance measurements
- 9 Activity wrist monitors will be collected from subjects at EOT visit of the Study MBGS205. If the activity wrist monitor was not performed before EOT of Study MBGS205 and collected at EOT Study MBGS205, it can be applied at the Baseline visit of current study and worn for 7 c consecutive days and collected at Visit 2. An activity wrist monitor will also be worn for 7 continuous days after Visit 7 (EOT) and collected at Visit 8 (FU)
- 10 Some questionnaires will be new for some subjects and completed first time at the Baseline visit
- 11 For subjects that discontinued early, EOT DEXA scan will be performed only if they reached minimum Week 36 (Visit 4) active treatment period. In order to accommodate scheduling, EOT DEXA can be performed within 5 days before the EOT visit or 5 days after the EOT Visit
- 12 [REDACTED]
- 13 AEs, SAEs, and AESIs collected from signature of informed consent

9.2 Discussion of Study Design

9.2.1 Risk/Benefit and Ethical Assessment

Refer to the most recent Investigator's Brochure (IB) for a benefit/risk assessment of BGS649.

Aromatase inhibitors decrease oestrogens, normalising LH, FSH, restoring physiologic hypothalamic, pituitary axis leading to normalisation in androgen levels. This is on-target pharmacology of aromatase inhibitors leading to benefit of treating symptoms of hypogonadism but also a clinical risk, as pharmacologic suppression of aromatase in men can cause androgens to rise above normal ranges (Loves et al 2008).

The emerging pre-clinical profile of BGS649 predicts multiple beneficial effects on the pathophysiology of HH. It is expected that the benefits of BGS649 will be similar to those of testosterone (standard of care treatment), including improvement in serum testosterone levels and hypogonadal signs and symptoms. It may also potentially improve fertility via restoration of LH and FSH feedback loops (see [Section 7.1](#) for further details).

Acute consequences of elevated androgens are rare; however chronic testosterone elevation can lead to elevation of haematocrit, effect on prostate and elevation of PSA and cardiovascular effects. Chronic suppression of oestrogens can also lead to worsening of bone mineral density. The study examines all potential adverse effects by evaluating bone density and other safety parameters on subjects exposed for 12 months and 6 months to BGS649.

Current study design allows 12 months benefit of study drug exposure (6 months from MBGS205 and 6 months from current study). To keep the study blinded and offer subjects receiving placebo the benefit of active arm treatment, the placebo subjects in Study MBGS205 will be randomised to one of the active treatment arms.

The most common side effects associated with BGS649 include headache, sweats, increased incidence of morning erections, nasal congestion, sore throat, cough, diarrhoea, musculoskeletal pain, insomnia and abnormal hair growth. Based on safety pharmacology studies in animals, BGS649 is not anticipated to cause cardiovascular, central nervous system or respiratory AEs. No significant corrected QT interval (QT_C) or QT_C by Fridericia's correction method (QT_CF) prolongation was observed in subjects across a wide range of doses up to 20 mg (see the IB). Therefore, a large therapeutic index is expected in humans.

Based on the benefit/risk profile of BGS649 in obese male subjects with HH, BGS649 is expected to normalise testosterone levels with very few adverse effects leading to all benefits of testosterone normalisation. BGS649 is also expected to decrease oestradiol with the potential risk of a reduction in bone mineral density and increased risk of fracture in subjects (see [Section 7](#)). Therefore, subjects will not be enrolled in the study if they have history of fragility fracture. In order to prevent potential premature withdrawals because of bone density deterioration, subjects with T score in pre-osteoporotic range and lower (T-score < -2.0) will not be allowed to participate. In addition, subjects will be monitored throughout the study and must be permanently withdrawn from study treatment if they develop fragility fracture (see

[Section 9.3.5](#)). An independent, unblinded external DMC will periodically review accumulating safety data (see [Section 16.3](#)).

9.3 Selection of Study Population

9.3.1 Inclusion Criteria

1. Participating in Study MBGS205 and completion of the 24 week treatment period without meeting any discontinuation criteria of Study MBGS205
2. Agreement on the part of the subjects to use double-barrier contraception for vaginal sexual intercourse with female partners of child bearing potential to prevent conception and foetal BGS649 exposure from seminal fluid. To use single barrier protection (condom) to prevent semen exposure through non-vaginal sexual intercourse with female partners of child bearing potential and refrain from sperm donation for the duration of the study. All to be continued for at least 3 months following study drug discontinuation
3. Ability to understand and comply with the requirements of the protocol/study, including understanding and being able to give informed consent
4. In opinion of the investigator has been compliant with the requirements of the Study MBGS205 protocol.

9.3.2 Exclusion Criteria

1. Development of clinically significant medical or psychiatric condition during Study MBGS205 that may interfere with the study assessments or mask/mimic symptoms of hypogonadism, would prevent the subject complying with the requirements of the protocol, or would make it unsafe for the subject to participate in the study as per investigator judgment
2. Development of hypothalamic or pituitary tumour (or inflammatory condition) or suspicion of pituitary or hypothalamic tumour based on a clinical or laboratory evidence, e.g., elevated prolactin or other pituitary hormone abnormality, symptoms/signs of tumour mass effect (unless there is documentation of a normal magnetic resonance imaging scan of pituitary and hypothalamus within 3 months before Baseline)
3. Meeting any of the discontinuation criteria of initial Study MBGS205
4. Evidence of new significant prostatic disease in Study MBGS205
5. Aspartate aminotransferase (AST) or alanine aminotransferase (ALT) > 3 times the ULN or bilirubin \geq 2 times the ULN (unless caused by Gilbert syndrome)
6. Fragility fracture or bone mineral density T-score < -2.0
7. Use of cardiac pacemaker or other medical electronic devices that can be affected by bio-impedance assessment
8. Planned treatment with prohibited medications (including self-prescribed)
9. 12-lead ECG abnormalities at Baseline including QT_CF interval > 450 ms
10. Intention to take part in study of other investigational product during the next 36 weeks.

9.3.3 Rescreening

Not applicable.

9.3.4 Study Drug Interruption and Discontinuation

Subjects may voluntarily discontinue investigational treatment for any reason at any time.

At the time of study drug discontinuation, the subject should have (as soon as possible) an EOT visit with the assessments that are normally done at the Week 48 visit (EOT, Visit 7). This should take place within 7 days after discontinuation of study drug. The reason for the discontinuation must be documented in the subject's medical records and entered on the appropriate electronic case report form (eCRF) page. All subjects who discontinue the study drug should enter the FU phase and attend the final follow up visit 12 weeks after EOT (FU, Visit 8).

Subjects will in addition be asked to provide a plasma and semen sample for PK at EOT (Visit 7), unless they are not able to provide this sample. This applies also to a subject discontinued because of elevated testosterone as determined by an unblinded physician. The investigator and study staff must discuss with the subject, the subject's continued participation in the study and request subjects to continue attending FU visits according to the study visit schedule.

If the subject cannot, or is unwilling to attend the FU visits, the site staff should request maintenance of regular phone contact with the subject, or with a person pre-designated by the subject. This phone contact should preferably be performed according to the study visit schedule. Data concerning the subject's health status, including information regarding new/concomitant treatments, AEs, AESIs (i.e., rash), and vital status will continue to be collected.

The investigator must also contact the IRT to register the subject's discontinuation from investigational treatment.

If the subject temporarily discontinues study drug because of AE or SAE or other relevant issue, the investigator should attempt to restart it as soon as possible after circumstances allow and in agreement with the Medical Monitor.

Investigational treatment MAY be permanently discontinued under the following circumstances:

1. Significant worsening of lower extremity oedema
2. Significant worsening of obstructive urinary symptoms

Investigational treatment MUST be permanently discontinued under the following circumstances:

3. If subject develops fragility fracture.
4. Total testosterone \geq 1500 ng/dL (52 nmol/L) at any 2 consecutive scheduled visits during and in between the both studies MBGS205 and MBGS206. This would also include situation when first testosterone value that meets this threshold of \geq 1500 ng/dL

[52 nmol/L] was measured during MBGS205 and consecutive testosterone during Study MBGS206.

5. Liver laboratory values of:

- ALT or AST > 5 times the ULN

If the increase in ALT or AST is associated with normal bilirubin and ALP, the medical evaluation of withdrawing a subject can be made on a repeat AST/ALT test taken within 48 hours. (Repeated parameters should include: ALT, AST, alkaline phosphatase and total bilirubin). The subject should interrupt study drug until the repeat liver enzymes are available. If repeat liver parameters are all within the normal range, dosing may be continued. If not normalised the subject should be permanently discontinued.

or

- ALT or AST > 3 times the ULN and bilirubin total > 2 times ULN or International Normalised Ratio (INR) > 1.5 or the appearance of worsening fatigue, nausea, vomiting, right upper quadrant pain/tenderness, fever, rash, or eosinophilia
- A hepatic event leading to subject discontinuation should be followed up until event resolution, or becomes not clinically significant

6. Any of the following laboratory abnormalities:

- Renal function values that require discontinuation:
 - Discontinue investigational treatment for a subject if individual serum creatinine increases $\geq 50\%$ compared to Baseline (and is considered clinically significant), or in the event of treatment emergent proteinuria (albumin: creatinine ratio > 300 mg/g or > 30 mg/mmol; protein: creatinine ratio ≥ 500 mg/g or > 50 mg/mmol) (Creatinine can be repeated once within 7 days of initial alert. Study drug administration should be suspended during this time and resumed only if repeat creatinine is back to pre-alert level)
 - A renal event leading to subject discontinuation should be followed up until event resolution (serum creatinine within 10% of Baseline, protein-creatinine ratio within 50% of Baseline), stabilises or becomes not clinically significant, or is assessed as being chronic

7. Subject missed 4 or more consecutive study drug dosing

8. Development of prostate cancer or PSA increase more than 1.4 ng/mL above Baseline level in study MBGS205. It is recommended that in these cases subjects undergo urologic consultation

9. Haematocrit > 54% (Haematocrit can be repeated once within 7 days of initial alert. Study drug administration should be suspended during this time and resumed only if repeat haematocrit is under 54%)

10. Development of sleep apnoea

11. Development of cardiovascular event (significant arrhythmia acute myocardial infarction, brain stroke, transient ischemic attack, unstable angina, congestive heart failure)
12. Emergence of the following AEs:
 - Absolute $QT_{cF} > 500$ msec, or a rise of QT_{cF} of ≥ 60 msec above Baseline confirmed by triplicate ECG measurements
13. Pregnancy in female sexual partner of the male study subject, occurring after the start of study treatment
14. Breast cancer.

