Hospitalisation is defined as at least 1 overnight formal admission into hospital, usually in order to perform additional tests, provide treatment which it is not possible to provide at home, and/or due to an unstable medical condition which requires specific monitoring of the subject. Pre-planned hospitalisations (known already prior to signing the ICF) will not be considered an SAE, unless any of the above criteria are fulfilled over the course of the hospitalisation due to unplanned complications. “Social” hospitalisation whereby it is administratively impossible to release the subject home is not necessarily an SAE. Complications that occur during hospitalisations are AEs. If the complication delays subject release from hospital, then the AE becomes an SAE.

4. Results in persistent or significant disability/incapacity

The term significant disability refers to any condition that impairs physical/physiological well-being to the extent that the subject is unable to function normally. Physical disability may include, but is not limited to, permanent disability of locomotion or motility, but also systemic permanent dysfunction including heart failure, liver insufficiency, or pulmonary fibrosis.

5. Is a congenital anomaly/birth defect

6. Is an important medical event

Important medical events that may not result in death, be life-threatening or require hospitalisation may be considered as an SAE when, based on appropriate medical judgement, they may jeopardise the subject, or the subject may require medical or surgical intervention to prevent one of the outcomes listed in this definition.

Treatment Emergent Adverse Event

Treatment emergent AEs (TEAEs) are defined as any AE occurring or worsening on or after the first dose of study medication administered during the study MBGS206

Adverse Events of Special Interest

Refer to [Section 12.1.7](#).

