12.1.7 Adverse Events of Special Interest

Some AEs, despite their severity or outcome, will be expedited due to the relevance for subject safety or study drug safety profile. These AESIs should be reported as expedited within 24 hours of awareness to ICON Pharmacovigilance and Safety Services:

1. Cardiovascular event (acute myocardial infarction, brain stroke, transient ischemic attack, unstable angina, congestive heart failure)
2. Prostate cancer
3. Lower extremity oedema \geq Grade 3 (which is not due to local pressure /venostasis effects such as may be caused by socks or other clothing).
4. Polycythaemia as measured by a haematocrit $> 54\%$
5. Fragility fracture
6. Development of sleep apnoea
7. Development of osteoporosis as per DEXA measurement (T score ≤ -2.5)
8. Breast cancer.

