12.1.8 Reporting of Serious Adverse Events and Adverse Events of Special Interest

Investigators and other site personnel must inform ICON Pharmacovigilance and Safety Services of any SAE/AESI that occurs during the course of the study whether or not considered causally related to the investigational product or to the study procedure(s): SAE from the time of informed consent until the 90 days after last dose of study drug, AESI from the time of randomisation until 90 days after last dose of study drug and within 24 hours of when he or she becomes aware of it.

Follow-up information on SAEs/AESIs must also be reported by the investigator within the same time frames.

If a non-serious AE becomes serious, this and other relevant follow-up information must also be provided to ICON within 24 hours as described above.

All SAEs/AESIs will also be recorded in the eCRF. The investigator is responsible for informing the Ethics Committee of the SAE/AESI as per local requirements.

Paper SAE/AESI forms should be completed at the site and faxed/mailed to the relevant ICON Pharmacovigilance and Safety Services or e-mailed to the global email distribution list within 24 hrs of awareness of the event.

SAE/AESI reports should be sent to:

[REDACTED]

If the report is sent via email, then the completed and signed SAE/AESI or Pregnancy report form must be attached to the email. A notification email of the event describing it in the email text is not sufficient.

Alternatively, the following fax number can be used for completed SAE/AESI reporting forms.

[REDACTED]

There may be situations when an SAE/AESI has occurred and the investigator has minimal information to include in the initial SAE/AESI report. However, it is very important that the investigator always makes an assessment of causality for every event prior to transmission of the SAE/AESI report form. Minimum criteria are identifiable subject (number), a suspect product (i.e., study drug or concomitant medication), an identifiable reporting source (investigator/study site identification), and an event or outcome that can be identified as serious or as an AESI. The investigator may change his/her opinion of causality in the light of follow-up information, amending the SAE/AESI report form accordingly. The causality assessment is one of the criteria used when determining regulatory reporting requirements for SAEs.

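### Protocol 9.3.4 equates AESIs with rash for men followed by phone, yet rash is not on the AESI list in 12.1.7 and the SAP gives no list to settle it

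*Protocol*

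**What the plan says.** **Definition.** Protocol 12.1.1 sends the reader to 12.1.7 for the meaning of AESI. Section 12.1.7 lists eight items: cardiovascular event, prostate cancer, lower extremity oedema of Grade 3 or above, haematocrit above 54%, fragility fracture, sleep apnoea, osteoporosis by DEXA, and breast cancer. It adds: "These AESIs should be reported as expedited within 24 hours of awareness to ICON Pharmacovigilance and Safety Services".

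**Phone follow-up.** Protocol 9.3.4 covers men who stop study drug early. "If the subject cannot, or is unwilling to attend the FU visits, the site staff should request maintenance of regular phone contact with the subject". Someone whom he has named in advance may be called instead. Among the data to be gathered this way, "AEs, AESIs (i.e., rash), and vital status will continue to be collected".

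**Cardiovascular wording.** AESI item 1 in 12.1.7 reads "Cardiovascular event (acute myocardial infarction, brain stroke, transient ischemic attack, unstable angina, congestive heart failure". Item 11 of the mandatory stopping criteria in 9.3.4 reads "Development of cardiovascular event (significant arrhythmia acute myocardial infarction, brain stroke, transient ischemic attack, unstable angina, congestive heart failure".

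**Start of the AESI window.** Protocol 12.1.8 sets reporting to pharmacovigilance as "AESI from the time of randomisation until 90 days after last dose of study drug". Footnote 13 of Table 9-1 says "AEs, SAEs, and AESIs collected from signature of informed consent".

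**Analysis.** AESIs form part of a secondary safety endpoint, together with AEs and SAEs (Protocol 13.4.2.1, SAP 4.2.1). SAP 8.7.4 tabulates and lists treatment-emergent AESIs. Neither that section nor the safety definitions in SAP 7.1.4 says which events qualify.

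**The concern.** The phone rule is an instruction to site staff, and the abbreviation it uses means that is, not for example. Taken literally, it tells staff that the special-interest event to ask about is rash. Rash is not on the AESI list. Its only other appearance in the stopping rules is as a symptom within the liver criterion.

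The placement adds to the difficulty. Six of the eight AESIs (cardiovascular event, prostate cancer, haematocrit above 54%, fragility fracture, sleep apnoea, breast cancer) are also mandatory reasons to stop drug under 9.3.4. Men off drug can therefore include men with bone or cardiovascular problems, and for those who do not attend visits the phone call may be the main source of later information.

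At stake is the classification of events as AESIs, and the 24-hour report for listed events that are not serious. Because the SAP has no list or derivation, nothing at the analysis stage is stated that would correct a site's flagging.

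**Working it through.** The plan states no figure on this point, so the check is mainly a comparison of passages.

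**1. The rash wording against the formal list.** Rash matches 0 of the 8 items in 12.1.7. Section 12.1.1 points only to 12.1.7. The protocol therefore has one definition and one gloss that contradicts it.

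**2. Does the phone period fall inside the AESI window?** Under 9.3.4, the End of Treatment visit should fall within 7 days of stopping, and the final follow-up visit 12 weeks later.
- 12 × 7 = 84 days after End of Treatment, so about 84 to 91 days after stopping.
- The AESI window in 12.1.8 closes 90 days after the last dose.

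Phone contact in this period lies almost wholly inside the window, so a listed AESI learned of by phone would still have to be expedited.

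**3. How many men?** The synopsis gives 30 men per previously active dose and about 17% dropout, aiming for about 25 completers.
- 0.17 × 30 = 5.1, so about 5 men per dose; 30 − 5 = 25, which agrees with the plan's target.
- Over three doses, this is about 15 of 90 continuing men.

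This is an upper bound. The same 5 include men who stop drug but still attend visits, men who withdraw consent (after which contact generally ends, 9.3.5) and men lost to follow-up (9.3.9). The documents do not give the split, nor the number of former placebo men per dose.

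**4. What one event is worth.** 1/30 = 3.3 percentage points on a dose group's AESI rate. This is the step size per event. It is not a forecast, because the plan gives no expected AESI rate.

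**5. The cardiovascular lists.** Section 12.1.7 names 5 conditions. Item 11 of 9.3.4 names the same 5 in the same order, preceded by significant arrhythmia, which makes 6. A man can thus be stopped for what 9.3.4 calls a cardiovascular event and have no cardiovascular AESI under 12.1.7.

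**6. The start points.** Table 9-1 puts confirmation of consent and treatment allocation at the same Week 24 visit, so the gap is short. Footnote 2 of that table says that only former placebo men are randomised in MBGS206. For the planned 90 continuing men (3 × 30), the start in 12.1.8 has no date of its own in this study.

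**The case against.** The strongest reply is that this is a stray parenthesis with little effect. The phone sentence also collects health status, new treatments, AEs and vital status. Protocol 12.1.2 requires every AE to be reported, and 12.1.8 does not exempt men followed by phone from AESI reporting. An event that caused a man to stop drug came before any phone follow-up and was already reportable. All men who stop early should have an End of Treatment visit and attend Visit 8, so the phone rule is a fallback. Protocol 13.5.1 treats every analysis as exploratory.

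All of this stands, and it limits the size of the problem. It does not make the instruction correct: the sentence names an event that is not on the list and none that is.

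Two stronger readings are tempting, and the documents do not support either.

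- A reader might infer that the protocol defines AESIs in three ways, counting item 11 of 9.3.4 as the third. That item is a stopping criterion and does not mention AESIs. The stopping and AESI lists also differ in both directions: the testosterone, liver, renal and QTcF criteria, missed doses and partner pregnancy are mandatory stops but not AESIs, while Grade 3 oedema and DEXA osteoporosis are AESIs but not mandatory stops. Only the near-identical wording under the same label calls for reconciliation.
- A reader might infer that the safety endpoint misses arrhythmia altogether. It does not. An arrhythmia is recorded as an AE and counted as treatment-emergent where it qualifies. If it ends treatment, it appears in the SAP 8.7.4 table of AEs leading to permanent discontinuation. If serious, it is reported within 24 hours. What it lacks is AESI classification and, if not serious, the expedited report.

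On the start points, it can fairly be said that 12.1.8 governs reporting and footnote 13 governs collection. The missing randomisation date for continuing men remains, but it is minor.

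**Conclusion.** The point holds in a limited form. The phone rule in Protocol 9.3.4 is wrong as written when read against 12.1.7, and the SAP does not repair it. The consequence is possible under-prompting, under-flagging or missed expediting of listed AESIs in a small subset: at most about 5 of 30 continuing men per dose, and probably fewer. General AE collection continues in these men. Each misclassified event would shift a 30-man group's AESI rate by 3.3 points.

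The size rests on two assumptions: that dropout is near the planned 17%, and that some early stoppers do not attend visits. That the AESI table would inherit a site's error further assumes that it is built from site flags, which the SAP neither states nor rules out.

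The cardiovascular mismatch is real and needs reconciling, but it does not show which list is in error. The difference in start points is minor.

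**What to change.** 1. In Protocol 9.3.4, replace the parenthesis on rash with a reference to the list in Section 12.1.7.
2. Have the sponsor reconcile the cardiovascular wording in 9.3.4 item 11 with AESI item 1 in 12.1.7, or state that the difference is intended. Which list is right is for the sponsor to decide.
3. Align the AESI start point in Protocol 12.1.8 with Table 9-1, so that it has a defined date for continuing men.
4. In SAP 8.7.4, state that treatment-emergent AESIs are derived from the 12.1.7 list, applied to all AEs irrespective of how a site flagged them. A list of MedDRA terms is not enough alone: the oedema, haematocrit and osteoporosis items also need the oedema grade, haematocrit and DEXA T-score data already collected.

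The cost is wording in a few protocol passages, one derivation in the SAP and some programming. No new data collection is needed. For data already collected, step 4 can be applied without a protocol change, though it cannot recover events that no one asked about by phone.
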